
90		4. Gender
91		5. Ethnicity
92		6. Weight
93		7. Height
94		8. BMI
95		9. Athletic participation
96		10. Primary sport
97		11. Hours per week in a barefoot sport
98		ii. History
99		1. Previous diagnosis of Sever's or calcaneal apophysitis
100		a. Brace previously used
101		
102		
103		4
104		
105		
106		
107		
108		
109		
110		
111		
112		
113		
114		
115		Figure 1. Cheetah Brace Figure 2. The X Brace
116		
117	C.	Description of Population to be Enrolled:
118		Barefoot athletes who present to sports medicine clinic for foot, ankle, or heel pain.
119		i. Inclusion Criteria:
120		1. Aged 7-14 years
121		2. Participate in barefoot sports including: martial arts, dance, gymnastics, or
122		acrobatics
123		3. A clinical diagnosis of Sever's or calcaneal apophysitis
124		ii. Exclusion Criteria:
125		1. History of foot/ankle surgery
126		2. History of rheumatologic diagnoses
127		3. Prisoners, pregnant females, individuals with limited decision-making capacity
128		
129	D.	Study Design and Research Methods
130		i. Human Subject Considerations
131		1. All patients will have an established relationship with a Children's Hospital
132		Sports Medicine Physician.
133		2. All PHI will be stored within REDCap.
134		ii. Study Design: Randomized Treatment Study
135		iii. Methods:

136	1. Subjects will be recruited face-to-face by a study team member at time of initial
137	visit, diagnostic clinical visit, or phone call initiated by [name]. Subjects
138	recruited via phone call will be patients of study personnel. Patients and
139	families interested in participating in the study will be contacted by a member
140	of the study team to set up a research only consent visit. If they cannot come
141	into clinic, the informed consent and assent will be sent to the family and a
142	research assistant with call the family, either via phone or video call, to go over
143	the consent and assent in real time and to answer any questions. After a signed
144	consent or assent form is received by the research assistant, the assigned brace
145	will be sent in the mail to the family and the associated questionnaires will be
146	sent via email.
147	2. Subject will be screened for inclusion/exclusion (enrollment) criteria by study
148	team member through chart review.
149	3. If subject meets enrollment criteria, they and a legal guardian will be consented
150	face-to-face by a study team member.
151	a. Consent will be sought from subjects ages 13-14.

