152	b. Assent will be sought from athletes younger than 13 years of age.
153	c. Consent will be sought from parents of subjects ages 7-14.
154	4. [name] or designated staff will answer any questions after the patient and
155	his or her parents have read and reviewed the informed consent and assent
156	forms. It will be emphasized to the patients that their decision to participate in
157	the study will in no way impact their treatment. Comprehension will be
158	assessed by reviewing the consent forms with the patient and his or her parents
159	thoroughly and asking the subjects questions requiring more than a simple
160	yes/no answer.
161	a. Patients and parents will sign the appropriate line on the informed
162	consent/assent form.
163	b. Consent procedures will take place in a private room or over a private
164	call.
165	5. Subject will complete initial demographics survey, OxAFQ-C, and VAS.
166	6. Subject will be randomized into either the Cheetah Heel Cup or The X Brace
167	treatment group. The randomization scheme will be independently created by
168	the research assistant. The random assignment will be kept blind to the PI and
169	statistician.
170	7. Subject will receive their assigned brace in the mail following their consent visit.
171	Subjects will receive an activity and rest log in the mail with their
172	brace. This is a weekly log and will help subjects track their weekly
173	activity in their barefoot sport (in hours), amount of time spent in
174	brace during barefoot sport (in hours), and any rest time taken from
175	their barefoot sport (in hours). This log is optional, but encouraged,
176	to fill out as it will not be submitted to the researchers. The
177	intended purpose of the log is to aid in answering the monthly
178	questionnaire on weekly activity, time in brace, and rest time.
179	8. At 1, 2, and 3 months, a study team member will email the subject's parent the
180	OxAFQ-C, VAS and questionnaire on activity/brace usage. During this time,
181	subjects will also answer questions pertaining to pain medicine use and any
182	adverse outcomes from brace use. A reminder phone call will be made if the

183 184 185 186 187		iv.	questionnaires have not been completed within 5 days. Subjects will not be seen after the visit where consent was obtained, unless an adverse outcome arises requiring an assessment by [name].Planned Duration of Study1. Two-years from COMIRB approval date to allow for adequate enrollment

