- 283 i. Sample Size: We will use a linear mixed model to test the null hypothesis that the 284 difference in OxAFQ-C physical domain scores between the The X Brace and 285 Cheetah Heel Cups does not depend on time (group*time interaction). Means for 286 treatment group at each time point were estimated based on a related RCT by James et al. ¹³. The common standard deviation for all OxAFQ-C physical domain 287 scores was assumed to be 6 and the correlation between time consecutive points 288 289 was conservatively assumed to be 0.6 based on this previous RCT. We intend to 290 use a one-to-one block randomization scheme to ensure equal allocation of 291 patients to each treatment group. Assuming a Type 1 error rate of 0.05, a sample 292 size of 44 participants total, 22 in each group, will provide 0.9 power to reject the 293 null hypothesis of no group*time interaction based on the Hotelling-Lawley test 294 statistic with an alpha level of 0.05. Assuming there is no missing data, no time 295 varying covariates, and the repeated measures are consistently collected (general 296 linear mixed model reversibility criteria is met), the Hotelling-Lawley trace statistic 297 is equivalent to the statistical test, the Wald statistic with Kenward-Roger degrees of freedom, described in the data analysis plan.²⁰. With an expected 30% loss to 298 299 follow up, we will inflate the sample size to account for attrition, for a total 300 enrollment goal of 58. The clinic treats 10 barefoot athletes with a clinical 301 diagnosis of Sever's Disease who meet the eligibility criteria for this study each 302 month. We expect a consent rate of approximately 50%. At an effective enrollment 303 rate of 5 patients per month, we will reach the enrollment goal of 58 participants 304 within 12 months. All samples size calculations were performed with GLIMMPSE, 305 an internet based open source software program capable of computing power and 306 sample size for multi-level and longitudinal research designs²¹
- 307 308
- 309

310 311 Table 1. Expected OxAFQ-C physical domain scores based on data from James et al^{13}

Treatment	1 month	2 months	3 months
Cheetah Heel Cups	67 (±6)	83 (±6)	85 (±6)
The X Brace	64 (±6)	82 (±6)	78 (±6)

312 313

314

315

316

317

318

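### The research assistant role creates the block list and handles consent on the remote route, with no concealment described, so the next brace may be known at enrolment.

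*Combined protocol and SAP*

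**What the plan says.** All steps below are in the combined protocol and SAP.

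- **List creation and blinding (Section IV.D.iii, step 6).** The wording is "treatment group. The randomization scheme will be independently created by" followed by "the research assistant. The random assignment will be kept blind to the PI and" the statistician. The research assistant is not among those kept blind.
- **Remote consent (step 1).** For families who cannot come to clinic, a "research assistant with call the family, either via phone or video call, to go over" the forms and answer questions.
- **Receipt of the form (step 1).** Once the "consent or assent form is received by the research assistant, the assigned brace" is mailed and the associated questionnaires are emailed. The sender of the brace is not named.
- **Screening and clinic consent (steps 2 and 3).** "Subject will be screened for inclusion/exclusion (enrollment) criteria by study" team staff through chart review. Consent is then taken "face-to-face by a study team member", whose role is not specified.
- **Type of randomization (Section IV.F.i, Sample Size).** The plan is to "use a one-to-one block randomization scheme to ensure equal allocation of" patients. No block size is given.

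No section describes sealed envelopes, central or web allocation, or a list holder separate from the person enrolling. Section IV.E presents REDCap as a tool for data capture and storage, not for allocation.

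**The concern.** Randomization protects the comparison only if the person bringing a family into the trial cannot know which brace comes next. Here one role writes the list and, on at least one route, also talks the family through consent and receives the form. Blinding the PI and the statistician does not address this. Nor does creating the list independently of them, since the person who needs to be unaware is the one enrolling.

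Foreknowledge leaves room for conscious or unconscious steering: which interested family is contacted next, how the trial is presented, or when a returned form is processed. The arms could then differ at entry in severity, motivation or expected recovery.

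This matters more than usual here because families know which brace they have, and pain and function are self-reported by emailed questionnaire. Concealment at entry is therefore an important safeguard, and it costs little to secure.

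**Working it through.** **1. Who does what, as written**

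| Task | Role named | Where |
|---|---|---|
| Create the list | the research assistant | IV.D.iii, step 6 |
| Kept blind | PI and statistician only | IV.D.iii, step 6 |
| Screen by chart review | study team member | IV.D.iii, step 2 |
| Consent in clinic | study team member | IV.D.iii, step 3 |
| Consent, remote route | a research assistant | IV.D.iii, step 1 |
| Receive signed form, remote route | the research assistant | IV.D.iii, step 1 |
| Mail the brace | not named | IV.D.iii, steps 1 and 7 |

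The overlap is explicit at the level of role, and only on the remote route. Nothing excludes it in clinic.

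**2. How predictable the next assignment is**

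Someone holding the list knows 100% of upcoming assignments. Someone who knows only past assignments and the block size is certain of the final run of identical assignments in each block. Block size is an assumption, because the plan gives none.

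- Size 2: 1 of 2 assignments is fixed = 50%.
- Size 4: of 6 sequences, 2 end in a run of two and 4 in a run of one. (2×2 + 4×1)/(6×4) = 8/24 = 33%.
- Size 6: of 20 sequences, 2 end in a run of three, 6 in a run of two and 12 in a run of one. (2×3 + 6×2 + 12×1)/(20×6) = 30/120 = 25%.

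**3. The plan's own figure, reproduced**

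Inputs from Section IV.F.i: alpha 0.05, SD 6, correlation 0.6 between consecutive visits, 22 per group. Table 1 gives between-group differences of 3, 1 and 7 points at months 1, 2 and 3.

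The Hotelling-Lawley test of group by time uses the successive changes in the group difference, θ = (3−1, 1−7) = (2, −6). It has 2 and 44−3 = 41 degrees of freedom and noncentrality λ = (22/2)·θ′V⁻¹θ, where V is the covariance matrix of the successive visit differences.

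- Compound symmetry: V has diagonal 2×36×0.4 = 28.8 and off-diagonal −14.4. λ = 11×56/43.2 = 14.26, power 0.913.
- AR(1): diagonal 28.8, off-diagonal −5.76. λ = 14.00, power 0.908.

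Both agree with the stated 0.9 power at 44 participants, so the same machinery can be used for bias.

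**4. Effect of a prognostic imbalance on the planned test, with no true brace effect**

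- *Constant over months 1 to 3:* θ = (0, 0), λ = 0, rejection rate 5%.
- *Linear from 0 at month 1 to s at month 3:* θ = (−s/2, −s/2). Then λ = 11s²/28.8 under compound symmetry and 11s²/46.08 under AR(1). For s = 1.2, λ = 0.55 and 0.34. For s = 1.8, λ = 1.24 and 0.77. For s = 3, λ = 3.44 and 2.15.

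Rejection rates, AR(1) to compound symmetry; every size and shape of imbalance is an assumption:

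| Imbalance at month 3 (points) | 1.2 | 1.8 | 3 |
|---|---|---|---|
| Constant over months 1–3 | 5% | 5% | 5% |
| One third, two thirds, all at months 1, 2, 3 | 6–7% | 7–9% | 12–17% |
| Linear from 0 at month 1 | 7–9% | 11–15% | 23–34% |
| Present at month 3 only | 9–10% | 15–18% | 35–44% |

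**5. A simple month-3 comparison, for contrast**

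SE = 6×√(2/22) = 1.81. A two-sample t test with 42 degrees of freedom and a shift of 1.2, 1.8 or 3 points rejects in about 10%, 16% or 37% of trials. This is not the planned primary test.

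**The case against.** A reader might infer more than the text supports, in three ways.

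- **That one person makes the list, enrols every family and sends out the brace.** The plan names a research assistant as the consenting person only for families who cannot attend; clinic consent and screening go to an unspecified team member. The caller is *a* research assistant and the list creator is *the* research assistant. One person is the natural reading but is not stated, and nobody is named as mailing the brace.
- **That the primary test's false-positive rate would rise to 10%, 16% or 37%.** Those rates belong to a month-3 t test. Hypothesis 1 does speak of a mean difference but names no visit, and Sections IV.F.i and IV.F.iii test only group by time, where a constant imbalance cancels.
- **That selection bias has occurred.** The documents show only that it is possible.

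The plan also has safeguards. Steps 2 to 5 place screening, consent and the baseline questionnaires before randomization in step 6. Eligibility rests on age, sport and a clinical diagnosis, which limits steering through the criteria. Section IV.F.iii provides intention-to-treat analysis and adjustment for imbalance.

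These points narrow the concern but do not remove it. The order of steps does not stop a list holder from knowing what comes next. On the remote route it is also loose, since both brace and questionnaires follow receipt of the form. Adjustment reaches only measured imbalances. Intention-to-treat analysis preserves the groups as randomized and cannot correct who was let into them. Steering by timing or presentation needs no bending of the criteria.

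**Conclusion.** The concern holds in a limited form. As written, the plan lets the role that creates the list also enrol on the remote route, keeps that role unblinded and describes no concealment. Foreknowledge of the next brace is therefore possible, and certain for anyone enrolling with the list in hand.

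The consequence for the primary test depends on the kind of imbalance: none if it is constant over months 1 to 3, and about 7–9%, 11–15% or 23–34% against a nominal 5% if it grows linearly from 0 at month 1 to 1.2, 1.8 or 3 points at month 3. These figures rest on the plan's SD and correlation, complete data on 22 per arm, and assumed imbalances. They illustrate sensitivity and do not estimate the bias to be expected. If the duties are already separated in practice, the gap is in the text alone.

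This is an improvement worth making because it is cheap and because analysis cannot restore concealment once unmeasured differences have entered.

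**What to change.** Amend step 6 of Section IV.D.iii, and align step 1 with it, so that:

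- the list is generated and held by someone who neither screens nor consents families, with varying block sizes not disclosed to enrolling staff;
- each assignment is released to the research assistant one at a time, through a locked allocation (for example in REDCap, if its set-up allows) or sequential sealed opaque envelopes;
- release happens only after eligibility, signed consent and assent, and baseline OxAFQ-C and VAS are recorded, on both the clinic and the remote route;
- the PI and the statistician stay blinded as planned.

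The cost is a short protocol edit, a one-off list set-up and one extra step before each brace is mailed. It needs a team member without family contact; the documents do not show that one is available, so this is an assumption. The 44 participants in the power calculation are unaffected. If the roles are already separate, a sentence saying so, together with the concealment method, is enough.

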188		۷.	Duration of Participation of Each Subject
189			1. About 30 active minutes for consent and surveys
190			2. About 3 months for course of clinical care and resolution of symptoms
191		vi.	Patient Incentives
192			1. Participants will receive a free brace after enrolling into the study. Upon
193			successful completion of the study (once month 3 survey is
194			completed), subjects will receive a \$30 gift card in the mail.
195	_		
196	Ε.	Descrip	otion, Risks and Justification of Procedures and Data Collection Tools:
197		١.	Potential Risks to Subjects:
198			I nere are no anticipated risks in this study beyond those of standard care and daily
199			living. There are no documented adverse outcomes associated with either brace
200			that is known to the study team. Any adverse outcomes (skin irritation/rash) that
201			anses during the study period will be documented during the monthly austion paires sont out to subjects. Additionally an unlikely and uncommon risk of
202			this study is that PHI may be unintentionally disclosed to an outside party. We will
203			nut forth our best effort to keep the information about subjects secure, and we
204			believe that the risk of accidental disclosure is minute. Identifying data will be
206			protected as per REDCap protocol after subjects have been assigned a study
200			number
208			
209		ii.	Plan to Protect Subjects/Mitigate Risks:
210			Subjects will be instructed to call the research assistant if any adverse outcomes
211			arise (skin irritiation/rash that causes discomfort or concern). The research
212			assistant will document the adverse outcome in REDCap, and relay the message
213			onto [name] who will contact the family to discuss the adverse event and if
214			any of the following is needed: a new brace size, discontinued use of the
215			brace/removal from study, a research visit to assess the adverse reaction. A
216			REDCap database will be utilized for the organization and storage of patient
217			information when necessary. Patients will be identified using individualized study
218			numbers that will be stored securely in the REDCap database. Data containing
219			spreadsheets will refer to patients only by the individualized study numbers,
220			excluding all PHI.
221			
222		iii.	Participant Discontinuation Criteria:
223			1. Subject participation will be discontinued if:
224			a. Subject no longer wishes to participate in the study

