225			b. Subject sustains an additional musculoskeletal injury or serious illness
226			(hospitalization, injury to lower body requiring a visit to
227			doctor).
220			c. subject fails to follow-up with clinical care.

229		d. Adverse reaction causing [name] to determine a discontinuation of
230		the brace.
231		
232	iv.	Data Collection Tools:
233		1. Demographic and clinical data will be collected from the subjects' charts from
234		EPIC and through subject input to REDCap questionnaires. REDCap will be used
235		to store all study data electronically. REDCap is a secure, web application
236		designed to support data capture for research studies. REDCap is hosted by the
237		University of Colorado-Denver Development and Informatics Service Center
238		(DISC).
239		2. The Oxford Ankle Foot Questionnaire for Children (OxAFQ-C) is used to measure
240		subjective well-being for child patients (aged 5-16) affected by foot and ankle
241		conditions using issues that are considered important to children. Typical
242		clinical assessments fail to capture the child patient's perspective and may not
243		accurately reflect how children function in their usual environments. The
244		OxAFQ-C was therefore designed to supplement clinical assessments to
245		evaluate the effectiveness of interventions for ankle/foot problems in children.
246		It is a short (15-item) questionnaire and reported as valid and reliable in
247		English ¹⁸ and Spanish and as responsive and longitudinally valid ¹⁹ . There are
248		three domains to the OxAFQ-C: physical, school and play, and emotional well-
249		being. Scores on the OxAFQ-C range from 0 to 100 with higher scores
250		indicating better functioning and higher well-being.
251		
252	۷.	Data Management:
253		1. Patients will be assigned patient study identifiers. These identifiers will be used
204		for the identification of all study materials, and will only be linked to the
200		patient's name, medical record number, or other PHI through REDCap. Non-
200		information will be stored with Dedeen. Dedeen is a secure web application
201		designed to support data capture for research studies, providing user friendly
250		web based case report forms, real time data entry validation (e.g. for data
209		types and range checks) audit trails and a de identified data event mechanism
200		to common statistical packages (SDSS_SAS_Stata_P/S_Dlus). The system was
201		developed by a multi institutional consortium which includes University of

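### Stopping the brace after an adverse reaction ends study participation, and nothing continues the month 1-3 questionnaires that the promised intent-to-treat analysis needs

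*Combined protocol and SAP*

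**What the plan says.** The Participant Discontinuation Criteria (IV.E.iii) open with "Subject participation will be discontinued if", and four criteria follow. Criterion d is an "Adverse reaction causing [name] to determine a discontinuation of" the brace. Under that stem, what ends is participation in the study.

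The Plan to Protect Subjects (IV.E.ii) describes what is discussed with the family after an adverse outcome: whether "any of the following is needed: a new brace size, discontinued use of the" "brace/removal from study, a research visit to assess the adverse reaction". Stopping the brace and removal from the study appear there as one item joined by a slash.

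Outcomes are collected remotely. Methods, step 8 (IV.D.iii) says: "At 1, 2, and 3 months, a study team member will email" the parent the OxAFQ-C, the VAS and a questionnaire on activity and brace use, with a reminder call if these are late. The same step adds: "Subjects will not be seen after the visit where consent was obtained, unless an adverse outcome" arises. It does not say what happens to the emails once a brace is stopped. Patient Incentives (IV.D.vi) ties the $30 gift card to "successful completion of the study (once month 3 survey is" done.

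The Analysis Plan (IV.F.iii) compares the arms across months 1, 2 and 3 in a linear mixed model. It promises intent-to-treat for the primary outcome variables and adds a per-protocol analysis.

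**The concern.** An intent-to-treat comparison needs outcomes whether or not the child is still wearing the brace. If stopping the brace also stops data collection, children who leave under criterion d have no later scores in either analysis. The period after stopping, where the intent-to-treat and per-protocol results should differ, is then unobserved.

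Criterion d matters most because it is defined by a reaction to the device, and the trial compares two devices. The exits can therefore differ by arm for reasons linked to treatment. The mixed model keeps scores collected before the exit, but it corrects only for what those scores explain. A child removed before month 1 has no score in the model at all, because only months 1 to 3 are modelled.

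Two results are exposed. A shift that grows or appears over time feeds into the group-by-time test. A shift that is equal at every month leaves that test unchanged but still moves the mean difference that Hypothesis 1 compares with 7 points.

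**Working it through.** **1. Reading the text.** The stem of IV.E.iii governs criterion d, so stopping the brace under d ends participation. IV.E.ii is consistent with this, though a slash is weak evidence. Step 8 sets the emails and contains no exception for children who have stopped. No other section supplies one. That later outcomes are lost is a fair inference rather than a stated rule; the consent pages are not in the copy reviewed.

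**2. Reproducing the plan's own figure.** The inputs are in IV.F.i and Table 1: arm differences of 3, 1 and 7 points, SD 6, correlation 0.6, alpha 0.05 and 22 per arm. For the two-group Hotelling test on the two time contrasts, with C the contrast matrix, δ the vector of differences and Σ the covariance matrix:

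- noncentrality = (n/2) · (Cδ)ᵀ (CΣCᵀ)⁻¹ (Cδ), with 2 and 2n − 3 = 41 degrees of freedom;
- compound symmetry: noncentrality 14.26, power 0.913;
- AR(1): noncentrality 14.00, power 0.908.

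The stated 0.9 power at 44 reproduces, so the same set-up is used below.

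**3. Assumed inputs.** The documents give no rate of removal under d. Assume that k = 1 to 3 children in one arm are removed after month 1. Assume also that their later scores differ from what their earlier scores predict by a gap of 3 to 6 points (0.5 to 1 SD). Enrolment is 58/2 = 29 per arm.

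**4. Shift in the arm mean.** Shift = (k/29) × gap, in either direction.

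- Smallest: (1/29) × 3 = 0.103 points.
- Middle: (3/29) × 3 = 0.310 points.
- Largest: (3/29) × 6 = 0.621 points.

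A simulation of 20,000 runs kept the month-1 score and estimated the month-3 mean by regression on it. It gave shifts of 0.102 to 0.107 and 0.619 to 0.623, which match the formula.

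**5. Against the standard error.** The SE of the month-3 difference at 22 per arm is 6 × √(2/22) = 1.809. The shift is then 0.103/1.809 = 0.06 to 0.621/1.809 = 0.34 standard errors.

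**6. Effect on the test and the interval.** The true difference is zero at every month, and the shift enters at month 3 only. Entering it at months 2 and 3 gives the same values.

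| Shift | Type I error, compound symmetry | Type I error, AR(1) | Coverage of 95% t interval (42 df) |
|---|---|---|---|
| 0.103 | 0.0504 | 0.0503 | 0.9496 |
| 0.310 | 0.0534 | 0.0527 | 0.947 |
| 0.621 | 0.0640 | 0.0609 | 0.937 |

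With 29 per arm the SE is 6 × √(2/29) = 1.576. At the largest shift the Type I error then reaches 0.069 and coverage falls to 0.933. A shift of equal size at all three months leaves the Type I error at exactly 0.05, but the mean difference still moves by the full shift.

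**The case against.** The strongest reply is that the effect may be trivial. Potential Risks (IV.E.i) says "There are no documented adverse outcomes associated with either brace" that the team knows of. The adverse outcome named is skin irritation or rash, and a new brace size is another option. Nothing shows that children stopped for a rash would differ by 0.5 to 1 SD beyond what earlier scores explain. Removals that are equal in both arms, with equal gaps, cancel. Even the largest shift, 0.621, is under 9% of the 7-point threshold (0.621/7 = 0.089), and these exits may already sit inside the planned 30% loss. All of this stands, and it limits the weight of the point. It does not show that exits are rare: Background (II) says no published studies of these braces exist, so the rate is unknown.

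A second reply is that intent-to-treat is compatible with incomplete follow-up, since a mixed model keeps all collected scores by assigned arm. That is correct under missing at random. The assumption is doubtful when exit follows a reaction to the device, and it does not help a child removed before month 1. The figures above do not cover that case.

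A third reply is that a child who stops one brace might obtain the other, so later scores could reflect the comparator. That is a fair caution about interpretation. Step 8 already asks about brace use, and recording what was worn after stopping would answer it.

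**Conclusion.** The concern holds, as a worthwhile improvement rather than a fatal flaw. By the wording of the protocol, criterion d ends participation, no section keeps the questionnaires going, and intent-to-treat is promised on exactly those scores. The loss can depend on the assigned brace and is largely avoidable, because outcomes come by email.

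The size is not known. Under the assumptions shown, at 22 per arm, the month-3 mean moves by 0.10 to 0.62 points in either direction, the Type I error is 0.050 to 0.064, and interval coverage is 95.0% to 93.7%. This rests on an assumed number of removals, all in one arm, an assumed gap, and the inference that questionnaires stop at removal. No direction of bias is claimed. Criteria b and c end participation in the same way, but dependence on the brace is not shown for them.

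**What to change.** Amend IV.E.iii and IV.E.ii to distinguish a child whose brace was stopped from a child withdrawn from the study. The clinical decision to stop a brace stays as it is.

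- After criterion d, keep emailing the existing month 1-3 questionnaires unless consent or assent is withdrawn. Do the same after b and c where the family is willing.
- Record the date and reason for stopping, and any brace worn afterwards.
- In IV.F.iii, state that scores after stopping enter the intent-to-treat mixed model. Use brace stopping to define the per-protocol set, and report removals by arm and criterion.
- Flag scores after a new lower-body injury (criterion b) and show results with and without them.
- Reconcile criterion c, which ends participation for not following up with clinical care, with step 8, which schedules no visits after consent.

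The cost is low: a short amendment, a few more emails and reminder calls, and a few more gift cards. With three children retained, as at the top of the illustration, the cards come to 3 × $30 = $90.

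### The enrolment goal of 58 does not cover the stated 30% loss: it leaves about 41 completers, not the 44 behind the 0.9 power; 63 (64 for equal arms) would be needed

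*Combined protocol and SAP*

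**What the plan says.** Everything on this point is in the Data Analysis Plan, item i (Sample Size).

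- **Size before attrition.** A "size of 44 participants total, 22 in each group, will provide 0.9 power to reject the" null hypothesis, which is the "null hypothesis of no group*time interaction based on the Hotelling-Lawley test" statistic at an alpha of 0.05.
- **Condition.** The powered test is equated with the planned Wald test with Kenward-Roger degrees of freedom under conditions that begin "Assuming there is no missing data, no time"-varying covariates and consistently collected measures.
- **Attrition.** The text continues "With an expected 30% loss to" and then "follow up, we will inflate the sample size to account for attrition, for a total" that the next line gives as "enrollment goal of 58. The clinic treats 10 barefoot athletes with a clinical" diagnosis.
- **Allocation.** The trial will "use a one-to-one block randomization scheme to ensure equal allocation of" patients to the two braces.

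No inflation formula is printed. No other attrition rate or rule appears elsewhere in the document.

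**The concern.** An attrition allowance has one purpose: to make sure that enough participants remain after the expected loss to support the stated power. Loss to follow-up is a fraction of those enrolled, so the number needed at the end is divided by the fraction expected to stay. Increasing the evaluable number by 30% is a different operation and always gives too small a target.

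Here 44, 30% and 58 cannot all be right together. A reader who takes the section at its word will believe that 58 enrolled children protect the 0.9 power against 30% loss, and the plan's own numbers say otherwise. The rate deserves to be taken seriously. All follow-up is by emailed questionnaire at 1, 2 and 3 months with a reminder call, and no visits are planned after consent, so nothing in the document supports planning for a lower loss.

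**Working it through.** **Inputs** (all from the Sample Size item and its Table 1): 22 per arm; alpha 0.05; SD 6 at every visit; correlation 0.6 between consecutive visits; expected means 67, 83, 85 (Cheetah) and 64, 82, 78 (X Brace), so differences of 3, 1 and 7 points; loss 30%; goal 58.

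**Assumption.** The correlation between months 1 and 3 is not given. I varied it from 0.30 to 0.60. The value 0.60 is compound symmetry, and 0.36 (0.6²) is first-order autoregressive.

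**1. Reproduce the 44 and the 0.9.** For two groups and three visits, the Hotelling-Lawley test of group-by-time is an F test with 2 and N − 3 degrees of freedom. Its noncentrality is n₁n₂/(n₁+n₂) × θ′S⁻¹θ, where θ holds the changes in the group difference between successive visits and S is their within-group covariance matrix.

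Under compound symmetry this has a simple form. The mean of 3, 1 and 7 is 3.667, and the squared deviations sum to 18.67. With 22 per arm the noncentrality is 11 × 18.67 / (36 × 0.4) = 14.26, which gives power 0.913. The plan's 0.9 is reproduced.

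**2. Reproduce the 58.**
- 44 × (1 + 0.30) = 57.2, rounded up to 58. This matches.
- 44 / (1 − 0.30) = 62.86, rounded up to 63. This does not match.

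**3. What 58 delivers.**
- Completers after 30% loss: 58 × 0.70 = 40.6, about 41, which is 3 to 4 short of 44.
- Largest loss that still leaves 44: 1 − 44/58 = 24.1%.

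**4. What 30% loss requires.**
- 63 × 0.70 = 44.1 completers; 64 (32 per arm) × 0.70 = 44.8.
- The printed goal is 5 to 6 children too low: (63 − 58)/63 = 7.9%.

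**5. Power on completers.**

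| Completers (per arm) | Month 1–3 correlation 0.60 | 0.50 | 0.36 | 0.30 |
|---|---|---|---|---|
| 44 (22/22) | 0.913 | 0.903 | 0.908 | 0.915 |
| 42 (21/21) | 0.898 | 0.888 | 0.893 | 0.900 |
| 41 (20/21) | 0.890 | 0.879 | 0.884 | 0.892 |
| 40 (20/20) | 0.881 | 0.870 | 0.875 | 0.884 |

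Except at the lowest correlation, 22 per arm is the smallest equal-arm size that reaches 0.9, so the design has almost no slack to absorb the missing completers.

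**6. Power if partial follow-up is used.** This is an information-based approximation for 29 enrolled per arm and 30% monotone loss in each arm, under the compound-symmetry and autoregressive structures. It takes the completer count for the denominator degrees of freedom:
- all loss before month 1: 0.88–0.89
- loss spread equally over no survey, month 1 only, and months 1–2 only: about 0.89
- all loss after month 2: about 0.91

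Using the enrolled count for the degrees of freedom instead adds about 0.01.

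**The case against.** Nobody disputes the arithmetic of 58, 30% and 44. The case on the other side is about consequence and reading.

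First, the planned analysis is a linear mixed model across months 1, 2 and 3 with an intent-to-treat analysis, so a child who answers early surveys and then leaves still contributes. Counting completers is the pessimistic reading, and if most loss comes after month 2 the 0.9 is essentially met. This stands as a limit on the size of the problem. It does not rescue the figure: children lost before month 1 add nothing to the model, those seen only at month 1 add little about change over time, and the section ties its power calculation to complete data rather than to recovery from partial data.

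Second, the power loss is small. Even on completers it is 1 to 2 points below the stated 0.9 with 41 children, and part of the apparent fall arises because 22 per arm slightly exceeds 0.9. This also stands.

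Third, multiplication by 1.3 is inferred. That is correct, since no formula is printed. The mismatch between 58, 30% and 44 does not depend on how 58 was reached.

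Fourth, the plan attaches 0.9 to the 44 and does not restate power after attrition. That is literally true, but the inflation has no purpose other than to preserve that power.

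**Conclusion.** The concern holds. The goal of 58 does not account for 30% loss: it leaves about 41 completers against the 44 on which the power statement rests, and it covers a loss of only 24.1%. The target consistent with the section's own figures is 63, or 64 with equal arms, so the printed number is about 8% low.

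The practical effect is modest. Completer power is about 0.88–0.89 with 41 children, against about 0.90–0.915 with 44. With partial follow-up it is roughly 0.88–0.91, depending on when children leave. The counts need no assumption beyond the plan's 30%. The power values also rest on Table 1, SD 6, consecutive correlation 0.6 and an assumed month 1 to 3 correlation; the partial-data range is approximate. The design and the choice of test are not affected. This is an enrolment figure that should be corrected as written.

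**What to change.** Correct the attrition sentence in the Sample Size item in one of two ways.

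- **Keep 58 and say what it gives.** For example: *58 children (29 per arm) with 30% loss leave about 41 completers, with power of about 0.88 to 0.89 on completers alone and up to about 0.91 if the mixed model uses partial follow-up from children who leave late; 44 completers are retained only if loss is at most 24%.* No extra children are needed. The cost is a slightly less favourable power statement.
- **Keep 30% and 44 completers, and print 63 (64 for equal arms).** At the stated 5 per month this takes 63/5 = 12.6 or 64/5 = 12.8 months, against 58/5 = 11.6 for the present goal. The claim of reaching the goal within 12 months would need changing, but recruitment still fits the planned two-year study.

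In either case, print the inflation formula so that the figure can be checked.
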